Non-Interventional Study Protocol

Study Protocol Number MS700568_0070

Title Oral CLADribine in patients that Change from first-line

Disease Modifying Treatments for Multiple Sclerosis: a

pROspective effectivenesS and Safety study

(CLAD CROSS)

Protocol version identifier 2.0

Protocol Date/Version 7 April 2021 / Version 2.0

Replaces Version v1.1

Active substance Cladribine

Medicinal product Cladribine tablets

Sponsor

Merck Hellas sa. [name]

Sponsor Legal Representative in the European Union Merck Healthcare KGaA, Darmstadt, Germany, an affiliate of Merck KGaA, Darmstadt, Germany [name]

objectives

Research question and The main aim is to study in the real world setting the effectiveness of Cladribine tablets in terms of ARR (Annualized Relapse Rate) and disability progression, in patients who switch from a first line DMD (Disease Modifying Drug) (Interferons, Glatiramer Acetate, Teriflunomide, DMF (Dymethyl fumarate)).

Primary Objective:

To study the change in annualized relapse rate (ARR) in patients switching from first-line DMDs to Cladribine tablets, between the 12-month pre-baseline period and over the 12 months period before End of Study follow-up (2 years)

Secondary Objectives:

- To assess change in annualized relapse rate (ARR) in patients switching from first-line DMDs to Cladribine tablets, between the 12-month pre-baseline period and over the 12 months period after initiation of Cladribine tablets (1 year)
- To assess disability progression 1
- To assess disability improvement 1
- To assess safety of Cladribine tablets in the real world setting. at two years
- To assess Quality of Life and treatment satisfaction

CONFIDENTIAL

INFORMATION

Disability progression is defined as progression on ≥1 of 3 components (EDSS, T25FW, and/or 9HPT) confirmed ≥24 weeks apart and with a ≥20% minimum threshold change for T25FW and 9HPT. Progression on EDSS is defined as at least I point in the EDSS score or an increase of at least 1.5 points if the baseline EDSS score is 0. Disability Improvement is defined as improvement on ≥1 of 3 components (EDSS, T25FW, and/or 9HPT) confirmed ≥24 weeks apart and with a \$20% minimum threshold change for T25FW and 9HPT. Improvement on EDSS is defined as a decrease in EDSS by at least 1 point (1.5 points if baseline EDSS was 1.5). T25FW and 9HPT are optional and will be performed if done as per routine practice.

Signature Page -	Principal Investigator50			
Sponsor Respons	ible Persons not Named on the Cover Page51			

2 List of Abbreviations

[figure not shown]
ADL	Activities of Daily Living				
ADR	Adverse Drug Reaction				
AE	Adverse Event				
AR	Adverse Reaction				
ARR	Annualized Relapse Rate				
CI	Confidence Intervals				
CNS	Central Nervous System				
CUA	Cumulative Unique Active				
CRF	Case Report Form				
CRO	Contract Research Organization				
DMD	Disease Modifying Drug(s)				
DMF	Dymethyl Fumarate				
EDC	Electronic Data Capture				
EDSS	Expanded Disability Status Scale				
ENCePP	European Network of Centres for Pharmacoepidemiology and Pharmacovigilance				
EU	European Union				
GA	Glatiramer Acetate				
GP	General Practitioner				
GVP	Good Pharmacovigilance Practices				
HCP	Healthcare Provider				
ICF	Informed Consent Form				
IEC	Independent Ethics Committee				
1FN	Interferon				
INN	International Nonproprietary Name				
IRB	Institutional Review Board				
МАН	Marketing Authorization Holder				
MRI	Magnetic Resonance Imaging				

L04AA40 MS700568_0070

Cladribine

MS	Multiple Sclerosis			
RRMS	Relapsing Remitting Multiple Sclerosis			
RMP	Risk Management Plan			
SAE	Serious Adverse Event			
SAP	Statistical Analysis Plan			
SmPC	Summary of Product Characteristics			
USA	United States of America			
TARB	Therapeutic Area Review Board			
TSQM	Treatment Satisfaction Questionnaire for Medication			

3 Responsible Parties

3.1 Responsibilities of the Investigator

The Investigator is responsible for the conduct of the study at his/her site. He/She will ensure that the study is performed in accordance with the protocol and will ensure the quality and integrity of data, following all applicable international and national guidelines.

This non-interventional study will not interfere with treatment prescription by investigators. Accordingly, the Investigator will decide in advance the best therapeutic strategy for each patient according to current practice, regardless of the potential participation of this patient in the study. Subsequently, if the prescribed treatment is in line with the study protocol, the Investigator will consider the possibility of including the patient in the study.

The Investigator is responsible for adverse reaction and/or laboratory abnormalities recording and reporting, as specified in Section 11.

4	Abstract

4	Abstract
Title	Oral CLADribine in patients that Change from first-line Disease Modifying Treatments for Multiple Sclerosis: a pROspective effectivenesS and Safety study
	(CLAD CROSS)
Rationale and background	Recently, the number of available disease-modifying therapies for treatment of relapsing-remitting MS (RRMS) has increased. However many patients treated with these agents continue to experience relapses and disease progression. Cladribine is a synthetic deoxyadenosine analog that acts in peripheral tissues, enters the CNS and is taken up by lymphocytes and phosphorylated by deoxycytidine kinase, resulting it targeted and sustained reductions of the T and B lymphocytes. In the Phase III CLARITY study treatment with Cladribine tablets given in short courses annually for 2 years significantly improved clinical and MRI outcomes. In the Phase III ORACLE-MS study, Cladribine significantly reduced the risk of clinically definite MS in patients with a first clinical demyelinating event compared with placebo.
	Study Rationale: The main aim is to study in the real world setting the effectiveness of Cladribine in terms of ARR and disability progression in patients that switch from a first-line drug (Interferons, Glatiramer Acetate, Teriflunomide, DMF). The Phase III ONWARD study has shown a significant reduction in ARR when comparing the pre-baseline treatment period with the Cladribine tablets treatment period. However the study allowed all IFNs as pre-baseline treatments and pooled them together in the analysis. It was also not powered to detect differences in ARR and it did not include other first line treatments (DMF and Teriflunomide) in the analysis. In the current study we want to evaluate the potential reduction in ARR associated with Cladribine tablets treatment, compared to the pre-baseline period, in patients receiving first-line disease-modifying drugs, who switch to Cladribine tablets according to the decision of their treating physician.
Research question and objectives	The main aim is to study in the real world setting the effectiveness of Cladribine tablets in terms of ARR and disability progression, in patients who switch from a first-line disease modifying drug (Interferons Glatiramer Acetate, Teriflunomide, DMF).
	Primary Objective:
	 To study the change in annualized relapse rate (ARR) in patients switching from first-line DMDs to Cladribine tablets, between the 12-month pre-baseline period and over the 12 months period before End of Study follow-up (2 years)

	Secondary Objectives:
	 To assess change in annualized relapse rate (ARR) in patients switching from first-line DMDs to Cladribine tablets, between the 12-month pre-baseline period and over the 12 months period after initiation of Cladribine tablets (1 year)
	• To assess disability progression. Disability progression is defined as progression on ≥1 of 3 components (EDSS, T25FW, and/or 9HPT) confirmed ≥24 weeks apart and with a ≥20% minimum threshold change for T25FW and 9HPT. T25FW and 9HPT are optional and will be performed if done as per routine practice. Progression on EDSS is defined as at least 1 point in the EDSS score or an increase of at least 1.5 points if the baseline EDSS score is 0.
	To assess disability improvement. Disability Improvement is defined as improvement on ≥1 of 3 components (EDSS, T25FW, and/or 9HPT) confirmed ≥24 weeks apart and with a ≥20% minimum threshold change for T25FW and 9HPT. T25FW and 9HPT are optional and will be performed if done as per routine practice. Improvement on EDSS is defined as a decrease in EDSS by at least I point (1.5 points if baseline EDSS was 1.5).
	 To assess safety of Cladribine tablets in the real world, at two years
	To assess Quality of Life and treatment satisfaction
	To assess treatment adherence
	CCI
Karana and American	
Study Design	This is a prospective, non-interventional, multicenter, Phase IV study in patients with a confirmed diagnosis of RRMS who switched from first-line DMDs (Interferons, Glatiramer Acetate, Teriflunomide, DMF) to treatment with Cladribine tablets in routine clinical practice.
Population	Inclusion Criteria:
	 Patients must voluntarily give written informed consent. Patients must read and fully understand the Informed Consent Form (ICF)
	2. Adult patients, Male or female patients ≥ 18 years old

- Patients with confirmed diagnosis of Relapsing-Remitting Multiple Sclerosis (RRMS) diagnosed by the treating physician according to applicable clinical practice guidelines (currently McDonald 2017 criteria), with high disease activity.
- 4. Patients should have been treated with the same first-line DMD (Interferons, Glatiramer Acetate, Teriflunomide, DMF) and at a stable dose for at least one year prior to switch to Cladribine tablets and should have been prescribed Cladribine tablets according to the decision of the treating physician and for any reason deemed necessary, prior to enrollment in the study. Any washout period and/or washout methods required before switching (such as elimination of Teriflunomide) must have been conducted, according to the decision of the treating physician.
- 5. Required history data should be available:
 - MS data for the 12-months pre-baseline period (annualized relapse rate)
 - MS Medication History (prior DMDs)
- Fulfilment of the indication for treatment with Cladribine tablets per standard of care in accordance with the local SmPC

Exclusion criteria:

Patients are not eligible for this study if they fulfill any of the following exclusion criteria:

- Contraindications to use of cladribine tablets according to the Summary of Product Characteristics
- Patients with history of alcohol or drug abuse that could potentially interfere with their participation in the study.
- 3. Patient that have received Cladribine in the past
- Concurrent participation in an investigational study in which patient assessment and/or treatment may be dictated by a protocol

Outcomes

Primary Endpoint

Difference in ARR between the pre-baseline 12-month period and over the 12 months period before End of Study follow-up (2 years).

Secondary Endpoints

 Difference in ARR between the pre-baseline 12-month period and over the 12 months period after start of cladribine (1 year)

Cladribine

	 Percentage of patients with 6-month disability progression (EDSS, T25FW, 9-HPT)² at the end of the study follow-up period (2 years).
	 Percentage of patients with 6-month disability improvement (EDSS, T25FW, 9-HPT)² at the end of the study follow-up period (2 years).
	 Occurrence of adverse events and of serious adverse events.
	 Quality of life (MSIS-29), Treatment Satisfaction (TSQM v1.4) and CCI
	 Treatment adherence, assessed as percentage of cladribine tablets taken versus prescribed dose
Variables	Demographics
	Medical History
	MS history
	Prior and current MS medication
	Reason for switching from first line DMD to Cladribine tablets
	 Therapy with Cladribine Tablets (date of administration and number of tablets taken versus prescribed dose)
	 Participation in a Cladribine Patient Support Program
	Relapse Count: ARR
	 Disability test: EDSS, Timed 25-Foot Walk, 9-Hole Peg Test (EDSS Plus)
	 Quality of life questionnaire: MSIS-29
	• CCI
	Treatment Satisfaction Questionnaire: TSQM v1.4

² Disability progression is defined as progression on ≥1 of 3 components (EDSS, T25FW, and/or 9HPT) confirmed ≥24 weeks apart and with a ≥20% minimum threshold change for T25FW and 9HPT. Progression on EDSS is defined as at least 1 point in the EDSS score or an increase of at least 1.5 points if the baseline EDSS score is 0. Disability Improvement is defined as improvement on ≥1 of 3 components (EDSS, T25FW, and/or 9HPT) confirmed ≥24 weeks apart and with a ≥20% minimum threshold change for T25FW and 9HPT. Improvement on EDSS is defined as a decrease in EDSS by at least 1 point (1.5 points if baseline EDSS was 1.5). T25FW and 9HPT are optional and will be performed if done as per routine practice.

	Safety [Serious Adverse Events (SAEs), Adverse Events of Special Interest (AESI) and Adverse Drug Reactions (ADRs)]
Data Sources	Data will be collected via an electronic case report form ((e)-CRF). In addition, paper questionnaires will be completed by the subject and then will be transferred into the (e)-CRF.
CCI	242 patients with confirmed diagnosis of Highly Active Relapsing-Remitting Multiple Sclerosis (RRMS) will be enrolled in the participating countries. CCI
Data Analysis	All endpoints will be presented by descriptive statistics for Baseline, 12-month, and End of Study assessments. Assessments done at 6-month and 18-months will be presented similarly. Quantitative (continuous) variables will be summarized with the use of descriptive statistical measures [mean value, standard deviation (SD), median, min-max, Q1-

Cladribine

Q3]. Qualitative (categorical) variables will be displayed as frequencies and percentages (N, %). The normality of distributions will be examined using the Shapiro-Wilk test in order to determine whether or not to use parametric methods for analysis. Primary Endpoint: Pre- and post-baseline ARR (2 years) will be compared by ANOVA or Wilcoxon signed-rank test if data is not normally distributed. The 95% Confidence Interval (CI) for the difference will also be presented. For Secondary and exploratory endpoints the following calculations and comparisons will be performed: Pre- and post- baseline ARR (1 year) will be compared by ANOVA or Wilcoxon signed-rank test if data is not normally distributed. The 95% Confidence Interval (CI) for the difference will also be presented. For all other secondary endpoints, 95% CI will be calculated for the result at each timepoint and for the differences whenever applicable, using appropriate methods. Milestones First Patient Signed ICF: Q4 2019 Last Patient Signed ICF: Q3 2022 Last Patient Last Visit (LPLV): Q3 2024 Clinical Study Report: Q2 2025

5 Amendments and Updates

Protocol amendment 1: version 1.1 dated 31 March 2020

- Administrative changes including updated SmPC language and Merck name

Protocol amendment 2: version 2.0 dated 7 April 2021

- Reduction of the sample size
- Addition of two interim analyses
- Remote PRO completion allowed when remote consent is authorized
- Extension of the recruitment period
- Administrative changes including updated wording to Eligibility Criteria #4 for clarity

6 Milestones

Milestone Planue	
Start of data collection	Q4 2019
End of data collection	Q3 2024
Final report of study results	Q2 2025

7 Rationale and Background

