# 14.3.1 Secondary Objective: Derivation and analysis of the Secondary Outcome 6-month Disability Progression

#### **Derivations**

Disability progression will be assessed using the Visit 4 data and comparing the results with Visit 3. As per definition, if Visit 4 and Visit 3 dates are not separated by at least 24 weeks, disability progression will be set to missing. Disability progression will be assessed if at least one assessment (EDSS, T25FW or 9HPT) is available. As per definition, disability progression will be derived as "Yes" if at least one of the below cases occur:

- Visit 4 EDSS is ≥1 point greater than Visit 3 EDSS if Visit 3 EDSS is greater than 0;
- Visit 4 EDSS is 1.5 or greater when Visit 3 EDSS is 0;
- 20% increase in the T25FW score (average of the two trials) from Visit 3 to Visit 4;
- 20% increase in the 9HPT score (The two trials for each hand are averaged, converted to the reciprocals of the mean times for each hand and then the two reciprocals are averaged) from Visit 3 to Visit 4.

If none of those cases occurred, disability progression will be set to "No".

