#### **Analysis methods**

No missing data imputation will be performed. The proportion of patients with 6-month disability progression at the end of study will be presented including associated 95% Clopper Pearson exact intervals.

Disability progression at Visit 1, Visit 2 and Visit 3 will also be presented and derived in the same way. A bar plot with disability progression from Visit 1 to Visit 4 will be presented. Additionally, the results for EDSS, 9HPT and T25FW scores will be presented descriptively by Visit, including an absolute and relative change from baseline and to the previous visit.

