# 14.4.1 Secondary Objective: Derivation and analysis of the Secondary Outcome 6-month Disability Improvement

#### **Derivations**

Disability improvement will be assessed using the Visit 4 data and comparing the results with Visit 3. As per definition, if Visit 4 and Visit 3 dates are not separated by at least 24 weeks, disability improvement will be set to missing. Disability improvement will be assessed if at least one assessment (EDSS, T25FW or 9HPT) is available. As per definition, disability improvement will be derived as "Yes" if at least one of the below cases occur:

- Visit 4 EDSS is ≥1 point smaller than Visit 3 EDSS if Visit 3 EDSS is greater than 1.5;
- Visit 4 EDSS is 0 when Visit 3 EDSS is 1.5;
- 20% decrease in the T25FW score (average of the two trials) from Visit 3 to Visit 4;
- 20% decrease in the 9HPT score (The two trials for each hand are averaged, converted to the reciprocals of the mean times for each hand and then the two reciprocals are averaged) from Visit 3 to Visit 4.

If none of those cases occurred, disability improvement will be set to "No".

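### Progression and improvement are derived independently on any one of three tests, so a patient with discordant tests counts in both percentages and no planned table shows how many do

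*Protocol*

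**What the plan says.** The protocol (Abstract, 8.2 and 9.1.2.2) gives two parallel definitions. For progression: "Disability progression is defined as progression on ≥1 of 3 components (EDSS, T25FW, and/or 9HPT) confirmed ≥24 weeks apart". For improvement: "Disability Improvement is defined as improvement on ≥1 of 3 components (EDSS, T25FW, and/or 9HPT) confirmed ≥24 weeks apart". Neither is conditional on the other. T25FW and 9HPT are optional.

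SAP 14.3.1 and 14.4.1 turn these into two yes/no flags. Each is 'Yes' "if at least one of the below cases occur". The improvement section then says: "If none of those cases occurred, disability improvement will be set to" 'No'. The interval is the same for both; for improvement, "Disability improvement will be assessed using the Visit 4 data and comparing the results with Visit 3", and the progression section makes the same comparison. Neither derivation looks at the other flag.

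Reporting is also separate. For progression: "The proportion of patients with 6-month disability progression at the end of study will be presented including associated 95% Clopper Pearson exact intervals". The improvement section has the matching statement. Neither document ranks the three tests, addresses a patient who meets both rules, or plans a cross-tabulation of the flags.

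**The concern.** The two percentages will be read side by side as the disability result. As planned, the improvement numerator can include patients who progressed on another test over the same six months, and the report would not show how many. Because the overlap in the main analysis needs an optional test, it would also vary with which sites perform T25FW and 9HPT. Protocol 9.7.3 recognises that the optional tests may cause bias and promises methods in the SAP. The methods in SAP 14.3.2 and 14.4.2 deal with missing components, not with components that disagree.

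**Working it through.** The plan states no progression, improvement or overlap rate, so there is no figure to reproduce. The check has four parts.

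**1. Rules applied to a patient.** EDSS 3.0 to 4.0 is a rise of 1 point from a Visit 3 score above 0, so progression is 'Yes'. T25FW 8.0 to 6.3 s is (6.3 − 8.0)/8.0 = −21%, so improvement is 'Yes'.

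**2. Possible states.** Let each measured test be worse, stable or improved.
- EDSS alone: 0 of 3 states set both flags.
- EDSS plus one timed test: 2 of 9.
- All three tests: 12 of 27. In 5 of the 12, EDSS is worse and improvement is 'Yes'.

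These are counts of logical states, not probabilities.

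**3. Sensitivity analyses.** The third and fourth use EDSS only, so they have no overlap. The second (non-responder) analysis behaves differently. Take a patient with EDSS only, 3.0 to 2.0. Improvement is 'Yes' and stays so under 14.4.2. Progression is 'No' with fewer than three tests available, so 14.3.2 resets it to 'Yes'. The patient is in both percentages with no optional test done.

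**4. Size, by illustration.** All inputs are assumptions: no true change, all three tests done, test-to-test CV 8-15% for T25FW and 6-10% for 9HPT, and a chance EDSS change of at least 1 point in 3-8% each way. 9HPT is treated as a time, with longer meaning worse. For a timed test:
- P(worse) = P(Z ≥ ln 1.2 / (√2·CV))
- P(improved) = P(Z ≤ ln 0.8 / (√2·CV))

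Middle case (CV 10% and 8%, EDSS 5%), components independent:
- T25FW: worse 0.0987, improved 0.0573. 9HPT: worse 0.0535, improved 0.0243.
- Progressed: 1 − 0.95 × 0.9013 × 0.9465 = 0.190.
- Improved: 1 − 0.95 × 0.9427 × 0.9757 = 0.126.
- Neither: 0.90 × 0.8440 × 0.9222 = 0.700.
- Both: 0.190 + 0.126 − (1 − 0.700) = 0.016, about 1 in 8 of the improved.
- EDSS worse and improvement 'Yes': 0.05 × (1 − 0.9427 × 0.9757) = 0.004, or about 1 patient if all 242 had all three tests.

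Share of improved patients who are also progressed (simulated):

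| CV T25FW / 9HPT, EDSS | Independent | Correlation 0.3 |
|---|---|---|
| 8% / 6%, 3% | 6% | 1% |
| 10% / 8%, 5% | 13% | 3% |
| 15% / 10%, 8% | 23% | 8% |

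EDSS worse with improvement 'Yes' reaches at most 0.08 × (1 − 0.8536 × 0.9427) = 1.6% of patients (last row, independent). In the middle row at correlation 0.3 it is 0.07%.

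**9HPT direction.** The SAP scores 9HPT as an average of reciprocals of time but counts a 20% increase as progression and a 20% decrease as improvement. A 20% higher reciprocal means times 1/1.2 − 1 = −17%, that is, faster. Read literally, a patient with EDSS 3.0 to 2.0 and peg times 20% shorter (score × 1.25) receives both flags although both tests improved. With this literal rule, the three cases at correlation 0.3 rise to about 9%, 20% and 30%.

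**The case against.** The strongest reply is that these are two separate descriptive endpoints and overlap breaks no stated claim. One test can improve while another worsens, and both can be true. The SAP plans no stable group and no net result, and section 9 limits confirmatory testing to the primary outcome. The tests are also summarised separately by visit, and the EDSS-only analyses cover the case of most concern. All of this stands, but by-visit summaries of each test cannot show discordance within a patient.

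Three stronger readings are tempting and are not supported.
- *The improvement definition is wrong and must exclude anyone who progressed.* The protocol does not say this. It would redefine a protocol endpoint, and under the SAP's 9HPT direction it would remove patients who truly improved.
- *About 1 in 8 improved patients have worse EDSS.* That figure counts any discordance, mostly T25FW against 9HPT, in one assumed case.
- *Overlap arises only where an optional test was done.* This holds for the main analysis but not for the non-responder analysis.

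The size is also open to challenge. Every CV, EDSS probability and correlation is assumed. At correlation 0.5 the share falls to 0.1-2.6%, and rare use of the optional tests lowers the count further. The illustration uses a single change between two visits, as the SAP derivation does; a confirmed change would give lower figures.

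**Conclusion.** The gap is real: the two flags can both be 'Yes' for one patient, and the planned tables cannot separate improved-only from mixed patients. It affects the main secondary analyses and the first two sensitivity analyses; the third and fourth are free of it. The primary ARR endpoint is untouched.

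The size is unknown and probably small. Under the stated assumptions, with 9HPT read as a time, about 6-23% of improved patients are also progressed with independent components and about 1-8% at correlation 0.3. The combination of worse EDSS and reported improvement is about 0-1.6% of patients. A reader might infer that the two percentages should sum with a stable group to 100%, but no such display is planned. The conclusion is limited to a missing display and to a 9HPT direction that has to be settled before that display can be read.

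**What to change.** 1. First correct the 9HPT direction in SAP 14.3.1 and 14.4.1. State whether the score is a time or a reciprocal of time, and make the direction and the 20% threshold match.
2. Keep both protocol definitions. Add to 14.3.1/14.4.1 one table of four exclusive categories (progressed only, improved only, both, neither) with Clopper-Pearson intervals, among patients for whom the flags can be derived. The two planned percentages can be recovered from it: progressed = progressed only + both, and improved = improved only + both.
3. Show the table by number of components measured, so that the influence of the optional tests is visible.
4. Report improvement with no component progressing as a supportive figure.
5. Note under the non-responder analysis that imputation alone can place a patient in both percentages.

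This should be settled before database lock, because a choice made after seeing the data would be post hoc. The cost is some SAP wording and one extra table from data already derived. The downside is that the supportive improvement figure will be slightly less favourable than the main one.
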